# 8.6.1 Blood Collection for Plasma MK-5592

Sample collection, storage, and shipment instructions for plasma samples will be provided in the operations/laboratory manual.

# 8.7 Pharmacodynamics

Pharmacodynamic parameters will not be evaluated in this study.

# 8.8 Future Biomedical Research Sample Collection

Future biomedical research will not be conducted in this study.

# 8.9 Visit Requirements

Visit requirements are outlined in Section 1.3 (Schedule of Activities). Specific procedurerelated details are provided above in Section 8.

# 8.9.1 Screening

All screening procedures outlined in the SoA must be performed within 14 days before enrollment into the study. Informed consent/assent must be obtained from the participant or legally acceptable representative of each participant before any study-specific procedures are performed other than those procedures conducted for the purpose of routine clinical care. Assent will be obtained from minors according to institutional practices. Before treatment assignment, potential participants must be evaluated to determine whether they fulfill the entry requirements as set forth in Sections 5.1 and 5.2. Local laboratory tests (pregnancy, hematology/chemistry, imaging, and mycology testing) will be used to evaluate eligibility criteria. Only potential participants with clinically acceptable results from all screening criteria are to be enrolled in the study.

# 8.9.2 Treatment Period Visits

# 8.9.2.1 Day 1 Visit

Day 1 procedures/assessments listed in the SoA must be performed before initiation of study therapy. Only hematology/chemistry and/or pregnancy tests are to be repeated if it has been more than 2 days or 1 day, respectively, since screening labs were performed. After confirming that all study inclusion/exclusion criteria are met, participant will be assigned a study allocation number by an IRT and POS treatment will be administered.

# 8.9.2.2 Treatment Period

All participants will initiate treatment with IV POS and may transition to oral POS after a minimum of 7 days on IV study treatment, as clinically indicated. Dosing selection and preparation are described in Section 4.3 and Section 6.2, respectively. Study visits in the treatment period will occur at Day 3 and Weeks 1, 2, 4, 6, 9 and 12. At these scheduled visits, procedures/assessments are to be performed according to the SoA.

# 8.9.2.3 End of Treatment (EOT) Visits

Participants who discontinue study therapy before 12 weeks should have an EOT Visit within 3 days after the EOT. If the EOT Visit falls within the window for a regular scheduled visit, the EOT Visit should occur instead of the scheduled visit and participants should complete all follow-up visits at 14 and 28 days after the last dose.

Every effort should be made, for participants who withdraw consent for participation or who are withdrawn from the study for any reason, to complete the EOT Visit as well as the final mortality assessment at Day 114.

# 8.9.3 **Post-Treatment Visits**

Participants will be required to return to the clinic approximately 14 days after the last dose of study treatment for the post-treatment visit. If the post-treatment visit occurs less than 14 days after the last dose of study treatment, a subsequent follow-up phone call should be made at 14 days after the last dose to determine if any AEs have occurred since the post-treatment clinic visit.

Participants will also be required to return to the clinic approximately 28 days after the last dose of study treatment for the post-treatment visit.

In addition, mortality data will be collected at Day 114 for all participants regardless of whether the participant discontinues study therapy early. If the Day 114 visit occurs after the 28-day follow-up visit, the mortality follow-up can be conducted by phone call.

### 9 STATISTICAL ANALYSIS PLAN

This section outlines the statistical analysis strategy and procedures for the study. Changes to analyses made after the protocol has been finalized will be documented in a supplemental SAP and referenced in the Clinical Study Report for the study. Post hoc exploratory analyses will be clearly identified in the Clinical Study Report.

### 9.1 Statistical Analysis Plan Summary

Key elements of the statistical analysis plan are summarized below; the comprehensive plan is provided in Sections 9.2 through 9.12.

Study Design Overview	A Phase 2, Open-Label, Non-Comparative Clinical Trial to Study the Safety and Efficacy of Posaconazole (POS, MK-5592) in Pediatric Participants Aged 2 to Less Than 18 Years With Invasive Aspergillosis
Treatment Assignment	Pediatric participants aged 2 to <18 years with IA will be allocated to receive POS (Day 1-7 IV formulation, Day 8-84 either IV, PFS or oral formulation). Participants will be enrolled into 2 age cohorts: Age Cohort 1 (2 to <12 years) or Age Cohort 2 (12 to <18 years).
Analysis Populations	Safety: All Participants as Treated (APaT).
	Efficacy:
	
 
Full Analysis Set (FAS) and
 
Responder Population
 

	Pharmacokinetics : All treated participants who receive at least 7 days of POS IV solution and have postdose PK sampling while on POS IV therapy (PK Analysis Population).
	Analysis populations are also defined in Section 9.5.
Primary Endpoint(s)	The primary safety endpoint is the proportion of participants in the APaT population who experience 1 or more treatment-related AEs during POS study treatment (IV or oral) plus 14 days of follow-up.
	There are no primary efficacy or pharmacokinetic endpoints.
Secondary Endpoints	• Proportion of participants in the FAS population with a favorable global clinical response (partial or complete response) at the Week 6 (Day 42) Visit, at the Week 12 (Day 84) Visit, and at the EOT Visit (if different).
	• Proportion of participants in the Responder Population who have a relapse of IA at any point after achieving favorable global clinical response through 28 days post-treatment.
	• Cmin, Cmax, and Tmax, based upon sparse PK sampling (peak and trough concentration).
	• Analysis of exposure-response (efficacy and safety) relationships.
	
 
Participants' categorical perception of palatability and acceptability of the PFS formulation.
 

Statistical Methods for Efficacy/Immunogenicity/ Pharmacokinetic Analyses	Efficacy endpoints- overall proportion of participants in the FAS population with a favorable global clinical response at the Week 6, the Week 12, and the EOT Visits – will be estimated and the corresponding 95% confidence interval (CI) provided using the Clopper-Pearson method.
	In addition, the overall proportion of participants in the Responder Population who had a relapse of IA through 28 days post-treatment will be provided along with other descriptive statistics.
	A population PK analysis will be conducted as described in a separate Modeling Analysis Plan based on population PK models developed from prior pediatric and adult PK data for each formulation. Model-predicted individual concentration-time profiles will be used to derive Cmax, Cmin, Cavg, AUC, and Tmax. PK parameters for POS (Cmax, Cmin, Cavg, AUC, and Tmax) derived from the population PK analysis will be listed and summarized by formulation using descriptive statistics and to be summarized in a separate report.

Statistical Methods for Safety Analyses	The APaT population will be used for safety analyses. The percentage of participants who experience drug-related AEs during the treatment period plus the first 14 days of follow-up will be provided along with the corresponding 95% CI using the Clopper-Pearson method.
Interim Analyses	There is no prespecified interim analysis planned for this open-label trial. However, interim reviews of safety and efficacy data will be conducted by the external DMC in accordance with its charter.
Multiplicity	No multiplicity adjustment is planned.
Sample Size and Power	The sample size was chosen based on clinical, not statistical, considerations.

# 9.2 Responsibility for Analyses/In-House Blinding

The statistical analysis of the data obtained from this study will be the responsibility of the Clinical Biostatistics department of the Sponsor.

This study is being conducted as a nonrandomized, open-label study, ie, participants, investigators, and Sponsor personnel will be aware of participant treatment assignments after each participant is enrolled and treatment is assigned.

### 9.3 Hypotheses/Estimation

Objectives of the study are stated in Section 3. There are no hypotheses in this study.

### 9.4 Analysis Endpoints

Efficacy, pharmacokinetic and safety endpoints that will be evaluated are listed below.

### 9.4.1 Efficacy/Pharmacokinetic Endpoints

### 9.4.1.1 Efficacy Endpoints

There are no primary efficacy endpoints in this study. Efficacy endpoints include:

- Proportions of participants in the FAS population who have a favorable global clinical response (partial or complete response), as assessed by the investigator using the definitions in Section 8.2.1 (Table 6), at the Week 6 Visit, Week 12 Visit, and EOT Visit.
- Proportion of participants in the Responder Population who have a relapse of IA at any point after achieving favorable global clinical response through 28 days post-treatment. Relapse is defined as the re-emergence of clinical, radiographic, or other relevant abnormalities indicating IA.

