Scheduled Day/ Week and Window	Days -14 to -1	Day 1	Day 3 (±1 day)	Wk 1 (Days 7- 9)	Wk 2 (Days 12-18)	Wk 4 (Days 25-33)	Wk 6 (Days 39-47)	Wk 9 (Days 60-68)	Wk 12 (Days 81-89)	ЕОТ	14 (+2) days after last dose	28 (+2) days after last dose	Day 114 (+7 days)	Unsch b	b. Procedures at unscheduled visits to be performed as clinically appropriate.
PFS: Assessment of palatability and acceptability				х	Х	Х	Х	Х	Х	X					For participants receiving PFS formulation, to be performed only on first and last days of PFS treatment.
Efficacy Procee	lures		•							•					
Assess global clinical response							X		Х	Х					
Diagnostic imaging	Xc	X d			X d	Xc	X d	X d		x	c Required for all sites of infection only at screening and EOT. d. At other visits, if clinical condition changes, additional imaging can be performed at the clinician's discretion.				

Study Period	Screening				Т	reatment						Follow-Up	1	Unsch	Notes
Visit Number/Title	1 Screening	2 Baseline	3	4	5	6	7	8	9	EOTª	10	11	12	Unsch	a. Participants who discontinue study therapy before Wk 12 should have an EOT Visit within 3 days after EOT.
Scheduled Day/ Week and Window	Days -14 to -1	Day 1	Day 3 (±1 day)	Wk 1 (Days 7- 9)	Wk 2 (Days 12-18)	Wk 4 (Days 25-33)	Wk 6 (Days 39-47)	Wk 9 (Days 60-68)	Wk 12 (Days 81-89)	ЕОТ	14 (+2) days after last dose	28 (+2) days after last dose	Day 114 (+7 days)	Unsch b	b. Procedures at unscheduled visits to be performed as clinically appropriate.
IFI assessment		Х	Х	Х	Х	Х	х	Х	Х	Х	Х	Х			MSG/EORTC criteria; details in Appendix 9.
Assessment of relapse											Х	Х			Relapse to be assessed only in participants who have achieved a favorable clinical response and have completed study treatment.
Mortality assessment			х	X	Х	х	Х	х	х	х	Х	Х	Х	х	Mortality to be assessed through Day 114 visit for all participants.

Study Period	Screening				Т	reatment				Follow-Up	)	Unsch	Notes		
Visit Number/Title	1 Screening	2 Baseline	3	4	5	6	7	8	9	EOTª	10	11	12	Unsch	a. Participants who discontinue study therapy before Wk 12 should have an EOT Visit within 3 days after EOT.
Scheduled Day/ Week and Window	Days -14 to -1	Day 1	Day 3 (±1 day)	Wk 1 (Days 7- 9)	Wk 2 (Days 12-18)	Wk 4 (Days 25-33)	Wk 6 (Days 39-47)	Wk 9 (Days 60-68)	Wk 12 (Days 81-89)	ЕОТ	14 (+2) days after last dose	28 (+2) days after last dose	Day 114 (+7 days)	Unsch b	b. Procedures at unscheduled visits to be performed as clinically appropriate.

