Sample for Aspergillus galactomannan EIA	х	Х	x	Х	Х	х	х	Х	х	х	Х	Х		х	If collected within 7 days of Day 1, can be used for screening purposes. Collect samples as clinically indicated.
Mycology testing (direct and indirect test)	x	X		X	X	X	x	X	X	x				x	Required at Screening, Wk 6 & 12, and EOT visits, unless clinically inappropriate. Additional optional testing, including Aspergillus PCR, will be performed as clinically indicated. See Appendix 9.

Study Period	Screening				Т	reatment						Follow-Up	1	Unsch	Notes
Visit Number/Title	1 Screening	2 Baseline	3	4	5	6	7	8	9	EOTª	10	11	12	Unsch	a. Participants who discontinue study therapy before Wk 12 should have an EOT Visit within 3 days after EOT.
Scheduled Day/ Week and Window	Days -14 to -1	Day 1	Day 3 (±1 day)	Wk 1 (Days 7- 9)	Wk 2 (Days 12-18)	Wk 4 (Days 25-33)	Wk 6 (Days 39-47)	Wk 9 (Days 60-68)	Wk 12 (Days 81-89)	ЕОТ	14 (+2) days after last dose	28 (+2) days after last dose	Day 114 (+7 days)	Unsch b	b. Procedures at unscheduled visits to be performed as clinically appropriate.
PK/Biomarkers	6														
Plasma PK assessment		Х		Х	Х	Х	Х	Х	Х	X				Х	
Abbreviations: A IFI = invasive fu (MK-5592); SA	Abbreviations: $AE =$ adverse event; $ECG =$ electrocardiogram; $BAL =$ broncho-alveolar lavage; $EIA =$ enzyme immunoassay; $EOT =$ end of treatment; $IA =$ invasive aspergillosis; IFI = invasive fungal infection; IRT = interactive response technology; IV = intravenous; PFS = powder for oral suspension; PK = pharmacokinetics; POS = posaconazole (MK-5592); SAE = serious adverse event; Wk = week.														

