# 8.2.2 Diagnostic Imaging

High-resolution CT scan is required for all participants with pulmonary sites of infection, as chest X-ray is deemed insufficient for assessment of pulmonary IA. Each site of infection identified during screening should be followed throughout the study by repeating the same type of scan and the same imaging modality. All imaging will be performed locally, and evaluation of infection will be recorded on the eCRF. Recording of imaging should include sufficient details to reflect use of the 2020 EORTC/MSG criteria to support the classification of IA.

At screening and end of treatment, diagnostic imaging is required for all sites of infection. Imaging can be conducted at other times if the clinical infectious condition changes relative to the previous assessment and repeat imaging is judged warranted by the clinician. If diagnostic imaging is conducted before Screening and within 7 days of Day 1, the results may be used for screening purposes.

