# 8.2.3 Mycology Testing

Mycology testing includes both histology samples and standard fungal cultures from all sites of suspected *Aspergillus* infection, as clinically appropriate. Mycology testing also includes galactomannan testing of plasma, serum, BAL, and CSF, as well as *Aspergillus* PCR testing of whole blood, serum, plasma, and BAL. Unless clinically inappropriate or not warranted due to the participant's health, condition or disease progression/regression, mycology testing may occur at the following visits: Screening, Week 6, Week 12, and EOT. Additional mycology testing will be performed as clinically indicated and should correlate with potential disease regression/progression. All fungal culture results (positive or negative) as well as all galactomannan and *Aspergillus* PCR test results (positive or negative) are to be recorded on the eCRF.

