# 8.2.5 Relapse Assessment

Relapse of IA infection will be evaluated only in participants who have achieved favorable clinical response. Relapse will be assessed by the investigator through 28 days following completion of study treatment in those participants who have achieved a favorable clinical response.

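### Relapse counts radiographic or other re-emergence through 28 days, but after end of treatment no imaging is required and galactomannan is discretionary, so subclinical relapse may be missed

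*Combined protocol and SAP*

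**What the plan says.** The Synopsis (1.1), Section 3 and Section 9.4.1.1 share one definition. In 9.4.1.1 it reads: "Relapse is defined as the re-emergence of clinical, radiographic, or other relevant abnormalities indicating IA". Any one of the three kinds of evidence is enough.

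On timing, Section 8.2.5 says: "Relapse will be assessed by the investigator through 28 days following completion of study treatment". The Schedule of Activities (SoA) places the relapse assessment at visits 10 and 11, which fall 14 and 28 days after the last dose. The denominator (Section 9.5.1) is the Responder Population: FAS participants with a favorable response at the end of study treatment. Section 9.6.1 plans a proportion with descriptive statistics and names no interval for it.

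The evidence available in that window is set out elsewhere:

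- **Imaging.** Section 8.2.2: "At screening and end of treatment, diagnostic imaging is required for all sites of infection". The SoA note is stricter: "Required for all sites of infection only at screening and EOT". At other times, Section 8.2.2 says: "Imaging can be conducted at other times if the clinical infectious condition changes relative to the previous assessment", provided the clinician also judges the repeat scan warranted.
- **Mycology.** Section 8.2.3: "mycology testing may occur at the following visits: Screening, Week 6, Week 12, and EOT". The SoA mycology row has no mark at visits 10 or 11.
- **Galactomannan.** This has its own SoA row, marked at visits 10 and 11, with the note "Collect samples as clinically indicated". Section 8.2.7 says that samples may be collected, and asks for all results up to the follow-up visit.
- **IFI assessment.** The SoA marks it at visits 10 and 11. Section 8.2.4 describes a review of signs and symptoms against the 2020 EORTC/MSG definitions.

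**The concern.** Response at end of treatment is judged with required imaging of every infected site. Relapse, which begins where that judgement ends, is judged without it. Someone who reads the definition will take the 28-day proportion as a rate in which all three kinds of evidence were sought. In practice a scan after end of treatment depends on a change in clinical condition, and an antigen test depends on a clinical indication.

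At stake is the claim about durability. This is the plan's only endpoint that asks whether a response lasts after treatment stops. If silent relapses go unobserved, durability will look better than it was measured to be, and the report will not show how many responders were tested at all.

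**Working it through.** The plan states no relapse rate to reproduce, so the main check sets the definition beside the schedule. The arithmetic after it is illustrative.

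**1. Where countable relapses fall.** Entry to the Responder Population needs a favorable response at end of treatment. In practice, then, a countable relapse occurs after the last required scan, and the gap covers essentially the whole observation window.

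**2. What is looked for at visits 10 and 11.**

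| Route in the definition | Source of evidence at 14 and 28 days | Status |
|---|---|---|
| Clinical | IFI and relapse assessments, directed examination | Scheduled |
| Radiographic | Imaging of infected sites | Not required; triggered by clinical change and clinician judgement |
| Other: culture, histology, PCR | Mycology testing | No scheduled visit; as clinically indicated |
| Other: galactomannan | Separate SoA row | Listed at both visits, but only as clinically indicated |

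**3. Can the IFI assessment fill the radiographic gap?** For pulmonary disease, no. The clinical criterion for pulmonary aspergillosis in Appendix 9 is a CT sign, and Section 8.2.2 calls chest X-ray insufficient. Without a CT, the visit cannot show that a lung lesion has regrown.

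**4. Can a responder carry a lesion without symptoms?** Yes. Table 6 admits a partial response with a reduction in lesion diameter of 25% or more. It also admits radiological stabilization (0% to 25% reduction) when all attributable symptoms have resolved. In such a child, regrowth might at first be visible only on a scan.

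**5. Size of the Responder Population.** Table 9 uses 15 participants; its intervals reproduce exactly with the Clopper-Pearson method (for example 6/15: 16.3% to 67.7%). Section 9.9.1 cites adult and adolescent response rates of 45% and 42%. At 40% to 45%:

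- 15 participants give 0.40 × 15 = 6.0 to 0.45 × 15 = 6.75, so about 6 to 7 responders.
- 30 participants give 0.40 × 30 = 12.0 to 0.45 × 30 = 13.5, so about 12 to 14.

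With 6 responders, one missed relapse moves the estimate by 1/6 = 16.7 percentage points; with 12, by 1/12 = 8.3 points.

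**6. Illustration of understatement.** Expected reported rate = true rate × (1 − share missed). Both inputs are assumptions.

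| Assumed true rate | 0% missed | 25% missed | 50% missed | 75% missed |
|---|---|---|---|---|
| 10% | 10% | 7.5% | 5.0% | 2.5% |
| 20% | 20% | 15% | 10% | 5% |

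The chance of seeing at least one relapse is 1 − (1 − reported rate)^n. With a true rate of 10% it falls from 46.9% (none missed) to 26.5% (half missed) for n = 6, and from 71.8% to 46.0% for n = 12.

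**7. Imprecision, for comparison.** With no relapse observed, the exact two-sided 95% upper limit is 1 − 0.025^(1/n): 45.9% for 0/6 and 26.5% for 0/12. This is a separate matter from under-ascertainment and is present even when every relapse is found.

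**The case against.** The strongest reply is that the schedule is not silent after end of treatment. Galactomannan counts as mycology under Section 8.2.3, appears in the SoA at both follow-up visits, and has 1 mL budgeted at each in Table 12. A positive result could qualify as another relevant abnormality. All participants are assessed against the EORTC/MSG definitions at every visit. Section 8.2.2 also says: "Each site of infection identified during screening should be followed throughout the study by repeating the same type of scan". Discretionary scans and cultures remain open to the investigator. The definition needs only one route and does not promise systematic testing of each.

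Much of this stands. A reader might infer that mycology stops at end of treatment, that the endpoint can detect only clinically evident relapse, and that the rate is therefore biased low. The documents do not support that. Galactomannan is listed in the window, discretionary tests could find some silent relapses, and no text gives the share that would be missed.

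It does not close the gap. The sentence on following each site sets no scan after end of treatment, and the SoA restricts the imaging requirement to screening and end of treatment. The galactomannan mark is qualified as clinically indicated.

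A second reply is that the effect is small beside the imprecision. With 6 responders, moving from 20% to 15% is 6 × 0.05 = 0.3 of a child, and to 5% is 6 × 0.15 = 0.9. That is fair, and it is why the remedy is mainly about description and reporting. But averaging over more children would not remove an understatement, and a descriptive rate should say what was observed.

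**Conclusion.** The point holds in a limited form. The definition admits radiographic and other evidence through 28 days, but the plan does not systematically seek that evidence after end of treatment. Subclinical relapse may be missed, and the likely direction is understatement. The documents do not allow the amount to be estimated: the 15% to 5% range rests wholly on an assumed 20% true rate and an assumed 25% to 75% missed, and with none missed there is no bias.

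Relapse is a secondary, descriptive endpoint in a trial without hypotheses, so the primary safety result, sample size and power are untouched. What changes is the claim about durability. Non-study antifungal treatment is also allowed after study treatment (Section 6.7). That complicates reading the 28-day rate and is a further reason to show the evidence behind each relapse call.

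**What to change.** 1. In Sections 9.4.1.1 and 9.6.1, and in the same words in the Synopsis and Section 3, describe the endpoint as investigator-assessed relapse with imaging after end of treatment only when clinically triggered. Changing the SAP sections alone would leave the definitions in conflict. A label such as clinically detected relapse would not fit, because item 3 could find relapse by antigen alone.
2. Tabulate each relapse by type of evidence (clinical, radiographic, mycological). Report how many responders had any imaging, and how many had any galactomannan result, after end of treatment.
3. In the SoA, make the galactomannan samples already listed at visits 10 and 11 required for responders who were galactomannan-positive at baseline.

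The cost is wording in four places, one table and a few more assays. Item 3 adds no blood to the budget: the 1 mL at each visit is within the 13 mL galactomannan total in Table 12, and 8 + 52 + 13 + 5.6 = 78.6 mL, the stated maximum.

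The price is a narrower durability claim. Two gaps remain and should be stated as limitations: purely radiographic silent relapse stays unmeasured, and responders who were not galactomannan-positive at baseline (including possible IA without mycological evidence) gain no required test.
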